1.1 Purpose and scope of the statistical analysis plan

This document details the proposed analysis of the main paper(s) reporting results from the trial Testing the Effectiveness of an Evening Blue-depleted Light Environment in the Acute Psychiatric Ward. These main paper(s) will follow the strategy set out here. Any deviations from the analyses outlined in this SAP will be described and justified in the final report of the trial, including the inclusion of any analyses suggested by journal editors and referees. Modifications will be carefully considered and, as far as possible, will follow the broad principles set out here.

First and foremost, this SAP describes the analysis of the primary and secondary outcomes. Subsequent exploratory analyses are also expected to follow the broad principles of this SAP but are not described in detail here. Additionally, there is a parallel study being conducted investigating the experience of staff employed on the wards and the analyses planned for this study are not covered here.

The details presented here shall not prohibit accepted practices, such as data transformation prior to analysis. When possible, such data management and modelling decisions will be undertaken prior to revealing the treatment allocation.

The final analysis strategy will be available on request when the principal papers are submitted.

1.2 Background and rationale for the trial

There is increasing recognition of the need to stabilize sleep-wake cycles in individuals with major mental disorders. As such, clinicians and researchers advocate for the use of interventions targeted at sleep and circadian dysrhythmias as an adjunct to the standard treatments offered for acute illness episodes of a broad range of diagnoses. This project explored the benefits of admitting individuals with major mental disorders to an acute psychiatric inpatient unit where changes in light exposure are integrated into the therapeutic environment of a new psychiatric unit.

1.3 Objectives

1.3.1 Primary objective

The trial will test whether the environment with programmable lighting conditions offers any additional benefits beyond those associated with standard treatment in an acute psychiatric inpatient unit. Specifically, participants will be allocated to a ward with a lighting system that produces an environment with blue-depleted evening light or to a ward with the same layout and facilities but lacking the new lighting technology. The main objective is to examine if there is any difference between groups in the mean duration of hospitalization.

1.3.2 Secondary and exploratory objectives

The secondary objectives of this trial are to explore whether the blue-depleted evening light conditions influences are particularly beneficial in certain diagnostic subgroups, as well as the effect on the level of symptoms, functioning, episodes of suicidality or aggressive behaviour, medication usage, and self-reported side effects differ between groups and whether a shorter duration of admission is associated with greater stability of sleep-wake cycles and circadian rhythms.

STATISTICAL ANALYSIS PLAN for BAB-study

2. Study design

2.1 Study design

This is a single-centre, unblinded, two-arm, parallel-group, pragmatic effectiveness randomised controlled trial (RCT).

2.2 Randomization and treatment assignment

A detailed description of the randomisation procedure can be found in the published protocol. Briefly, there will be a 1:1 block randomisation with varying block sizes, using the webCRF program (developed and managed at the Clinical Research Unit Central Norway). Patients who may need admission to the acute psychiatric hospital unit will initially be assessed by other health professionals (general practitioners, out-of-hours emergency services, and other somatic and psychiatric hospital departments). If hospitalisation is deemed necessary, patients will be directed to the acute admissions facility. For the purposes of the trial, patients will be randomised prior to arrival at the unit (i.e. prior to any psychiatric assessment at the acute unit). Clinical considerations may mitigate against following the random allocation procedure, in which cases some participants may be withdrawn immediately from the trial (see section §3.2.2).

2.3 Determination of sample size

The sample size calculation is described in detail in the published protocol¹.

2.4 Framework

This trial is designed to establish the superiority of blue-depleted evening lighting environment compared to normal lighting on the duration of admission to acute psychiatric wards:

- The primary null hypothesis is that the duration of admission does not differ between the lighting environment group
- The primary alternative hypothesis is that the duration of admission differs based on the lighting environment.

There is only one primary outcome in this trial. The other efficacy analyses will be regarded as secondary or exploratory.

2.5 Statistical interim analyses

No interim analyses were planned or performed.

2.6 Timing of final analysis

Data was collected until 14 days after the last participant was randomised. Participants who were still admitted at this time were considered as discharged with their length of stay ending on this date.

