2.7 Data sources and timing of endpoint assessments

The primary outcome is duration of admission which is assessed upon discharge. Other secondary and exploratory outcomes are assessed either daily or upon discharge (See Table 1 in the published protocol¹). Data will be obtained from two main sources: Electronic patient records and Xethru radar sensors as described in the published protocol.

The Xethru radar sensors will be used to obtain data on each patient's sleep-wake cycle. As described in the published protocol, developed algorithms will be used to estimate the total sleep time (TST), sleep onset latency (SOL), number of nocturnal awakenings (NW), wake after sleep onset (WASO), and sleep efficiency (SE%)².

STATISTICAL ANALYSIS PLAN for BAB-study

3. Statistical principles

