3.3.2 Per-Protocol Analysis Set

The per protocol analysis set will include all participants in the ITT population who were hospitalised for at least two consecutive evenings, and who had no protocol deviations (§3.2.3).

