4.1 Screening data, eligibility, recruitment and withdrawal

All participants admitted during the trial period will be randomised. A Consolidated Standards of Reporting Trials (CONSORT) flow diagram will be used to summarise the number of participants as shown in the published protocol. Reasons for withdrawal post-randomisation will be summarised per treatment arm.

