5.1 Analysis of primary outcome

The primary outcome is duration of admission in days in the ITT population. Some patients will be readmitted and re-randomized during the study period. As such, we plan to use a two-level linear mixed-model with duration of stay as dependent variable, with admissions within patient as level 1, and patient as level 2. The primary covariate is group (blue-depleted evening lighting versus normal lighting condition). We will adjust the analyses for a set of pre-specified baseline variables which can be strong predictors of the outcome, as generally recommended by Kahan et al³ and Vittinghoff et al⁴.

These covariates are:

- Age
- Sex
- Diagnosis (categorized as psychotic episodes/disorders, manic episode, severe depressive episode, or none of these)
- Comorbidities (categorized as alcohol/substance use disorders, borderline or other personality disorders, or none of these two)
- Involuntary versus voluntary status at admission
- Number of admissions in the previous 2 years
- Number bed-days in the previous 2 years.

If the model fails to converge using a two-level model we will consider a single-level model.

As this primary outcome is heavily skewed and not normally distributed, we anticipate the use of bootstrapping with the bias-corrected and accelerated (BC_a) method and B=5000 bootstrap samples. If this results in unpractical long computing time, we will use a lower number of bootstrap samples, such as B=1000.

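### Stays still open at data cut-off enter the primary model as completed stays, with no per-arm count and no censoring-aware check (minor, affects the reported effect size)

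*SAP*

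**What the plan says.** Section 1.3.1 sets the target: "The main objective is to examine if there is any difference between groups in the mean duration of hospitalization". Section 2.7 states how the outcome arises: "The primary outcome is duration of admission which is assessed upon discharge". It also names the sources: "Data will be obtained from two main sources: Electronic patient records and Xethru radar sensors as described in the published protocol".

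Section 2.6 stops data collection 14 days after the last randomisation and adds: "Participants who were still admitted at this time were considered as discharged with their length of stay ending on this date".

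Section 5.1 gives the primary analysis: "we plan to use a two-level linear mixed-model with duration of stay as dependent variable". It has a single-level fallback for non-convergence and a BCa bootstrap, the latter introduced with "As this primary outcome is heavily skewed and not normally distributed". Neither marks a stay as incomplete.

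Section 5.1.1 rests the outcome on recorded admission and discharge dates and expects no missing values. It does not refer to section 2.6. Section 5.1.3 adds only a repeat in the per-protocol set, which section 3.3.2 defines thus: "The per protocol analysis set will include all participants in the ITT population who were hospitalised for at least two consecutive evenings", provided they had no protocol deviation. On flow reporting, section 4.1 plans a CONSORT diagram and says: "Reasons for withdrawal post-randomisation will be summarised per treatment arm".

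**The concern.** A patient still in hospital at cut-off has a true stay longer than the recorded one, so the value is right-censored. A linear model for the mean that takes it at face value understates that arm's mean. The bootstrap deals with skewness and the fallback with convergence; neither deals with censoring. The per-protocol repeat does not exclude cut stays, so it carries the same values. A deemed discharge is not a withdrawal, so the withdrawal summary would not show it.

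At stake is the size of the effect on the only primary outcome. The cut falls on long stays, which weigh heavily in the mean of a skewed outcome. As planned, the report need not say how many stays were cut or in which arm.

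**Working it through.** **No figure to reproduce.** The SAP refers to the published protocol for the sample size (section 2.3) and states no accrual length, mean, SD or effect. From the SAP come the 14-day minimum follow-up, the 1:1 allocation and the two-sided 5% level. The rest is assumed.

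**Assumptions.** Randomisation is uniform over A = 182 or 365 days, at r = 1 or 3 per day. Control stays L are lognormal with mean/SD of 6/8, 8/12 or 12/18 days. Stays are treated as independent.

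**Formulas.** A stay's follow-up c is uniform on (14, 14 + A). With mean m, σ² = ln(1 + SD²/m²) and μ = ln m − σ²/2:
- Share cut = average over c of P(L > c).
- Loss in an arm's mean = average over c of E[(L − c)+], where E[(L − c)+] = m·P(Z > (ln c − μ − σ²)/σ) − c·P(Z > (ln c − μ)/σ).
- Shift in the difference = control loss − intervention loss.
- Unadjusted standard error = √((SD_C² + SD_T²)/n), with n = A·r/2 per arm.

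**Scenario (a): intervention shortens every stay by 20%.**

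| Control mean/SD | True difference (days) | Shrinkage, A = 182 | Shrinkage, A = 365 |
|---|---|---|---|
| 6/8 | 1.20 | 0.040 (3.3%) | 0.020 (1.7%) |
| 8/12 | 1.60 | 0.110 (6.9%) | 0.057 (3.6%) |
| 12/18 | 2.40 | 0.285 (11.9%) | 0.151 (6.3%) |

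For 12/18 with A = 182, the losses are 0.680 (control) and 0.396 (intervention) days, a shift of 0.285 before rounding of the two losses. With r = 3, n = 273 and the SDs are 18 and 14.4, so SE = √((324 + 207.36)/273) = 1.395 and 0.285/1.395 = 0.204. Over the grid the shift is 0.027-0.204 SE, the share cut is 0.2%-2.0%, and the expected number cut is 0.8-11.0.

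**Scenario (b): only stays under 14 days are shortened.** No such stay can be cut, so the difference does not change.

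**Scenario (c): intervention mean 10% lower, log-variance 1.5 times larger.** The heavier tail loses more, so the difference grows. For 12/18 a true 1.20 becomes 1.589 (A = 182) or 1.452 (A = 365). For 6/8 a true 0.60 becomes 0.686 or 0.647. In the worst case the intervention SD is about 23.8, so with r = 3, SE = √((324 + 23.8²)/273) = 1.81 and the shift is 0.389/1.81 = 0.215 SE. Over the grid it is about 0.05-0.22 SE. With a 20% lower mean and the same inflation, the change is only +2.0% to +6.5% of the true difference.

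**Effect on inference.** The simulation used 4,000 trials, 12/18, A = 182, r = 3, and a Welch test on independent stays in place of the adjusted mixed model with BCa bootstrap.

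| Case | Full stays | Cut stays |
|---|---|---|
| Same distribution: type I error | 4.3% | 4.3% |
| (a): power | 42.7% | 47.0% |
| (a): 95% CI coverage | 95.1% | 93.6% |
| (a): root-mean-square error (days) | 1.38 | 1.17 |
| (c): 95% CI coverage | 95.0% | 93.2% |
| Equal means, log-variance ×1.5 in one arm: rejection | 5.6% | 8.7% |

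**Outside this range.** With 90 days of accrual, a control mean of 20 days and SD of 30, and a 20% proportional shortening, 10.1% of control and 7.3% of intervention stays are cut, and a true difference of 4.00 days appears as 2.63. The effect therefore grows when stays are long relative to accrual.

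**The case against.** The rule is stated openly and applied by calendar date, alike in both arms, and every stay has about 14 days of possible follow-up. When the arms are alike the test keeps its level. Under proportional shortening, power and root-mean-square error are slightly better with the rule than without it. All of this stands, and it is why the point is minor.

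Scenario (c) can be made to look alarming: 0.389 of 1.20 days is 32.4%. That is a percentage of a small difference, and nothing in the SAP suggests a lower mean with a much heavier tail. In standard errors it is of the same order as (a). The 8.7% rejection rate likewise needs equal means with unequal tails. The simulation is also a stand-in for the planned model.

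A reader might infer that sections 2.7 and 5.1.1 contradict section 2.6, or that the outcome has hidden missing values. The text does not support that. Every stay receives a value; the deemed end date is simply not a recorded discharge, and the absent cross-reference is editorial. Section 3.3.2 does not restate the cut-off rule either: it is silent, and the rule carries over by inference. Finally, the flow diagram follows a protocol that is not at hand, so it might show open stays. The SAP itself does not ask for it.

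What the objection does not remove is that the SAP itself fixes both the cut-off rule and a mean model that ignores it, and provides nothing by which a reader could judge the result.

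**Conclusion.** The point holds as a minor issue about the reported effect size. Open stays are lower bounds analysed as completed durations, so both arm means are biased down. A proportional effect is attenuated; with different tails the direction can differ, so attenuation should not be presumed.

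Under the assumed inputs the shift is about 0.03-0.22 of the unadjusted standard error, except in (b), where it is zero. The SAP cannot confirm that range, and much longer stays or shorter accrual would make the effect larger.

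Two stronger readings are tempting and not supported. One is that the rule invalidates the primary test: type I error is not materially affected when the arms have the same distribution. The other is that it generally exaggerates the benefit: that needs a specific tail pattern for which the SAP gives no evidence.

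**What to change.** For stays open at cut-off, take the actual discharge date from the electronic patient records that section 2.7 already names, if consent and approvals cover dates after the cut-off. Under scenario (a) this is a look-up for about 1 to 11 stays and keeps the target of section 1.3.1.

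If that is not possible, keep the primary model, report the number of cut stays per arm, and add one sensitivity analysis that treats them as right-censored and respects admissions within patient. A censored regression that allows for the skewness would do. A restricted mean with bootstrap resampling by patient is also possible, with its horizon stated and a note that it targets a narrower quantity. It does not recover the overall mean. Under scenario (a), for 6/8, 8/12 and 12/18, a 60-day horizon keeps 97%, 92% and 85% of the full difference, thus dropping 3%, 8% and 15%, about as much as the cut-off rule or more. A 28-day horizon keeps 87%, 76% and 63%.

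As an editorial step, cross-refer sections 2.7 and 5.1.1 to section 2.6.

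The cost is SAP wording plus either a short look-up, which may need confirmation of approvals because section 2.6 describes collection as closed, or one extra model. No new patients are needed.

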2.7 Data sources and timing of endpoint assessments

The primary outcome is duration of admission which is assessed upon discharge. Other secondary and exploratory outcomes are assessed either daily or upon discharge (See Table 1 in the published protocol¹). Data will be obtained from two main sources: Electronic patient records and Xethru radar sensors as described in the published protocol.

The Xethru radar sensors will be used to obtain data on each patient's sleep-wake cycle. As described in the published protocol, developed algorithms will be used to estimate the total sleep time (TST), sleep onset latency (SOL), number of nocturnal awakenings (NW), wake after sleep onset (WASO), and sleep efficiency (SE%)².

STATISTICAL ANALYSIS PLAN for BAB-study

3. Statistical principles

3.1 Confidence intervals and p-values

All efficacy and safety estimates will be presented with two-sided 95 % confidence intervals. Accompanying two-sided p-values will be calculated and compared to a 5 % significance level. No adjustments for multiplicity will be made since there is only one primary null hypothesis in this trial. This is in line with “Guideline on multiplicity issues in clinical trials EMA/CHMP/44762/2017”.

3.2 Adherence, protocol deviations and protocol violations

Randomised individuals may withdraw or be withdrawn from the allocated treatment group for various reasons as outlined in the published protocol, or they may not be adherent to the light conditions. The published protocol did not distinguish between withdrawals from the intention-to-treat and per protocol analyses, which are clarified in the following sections.

3.2.1 Adherence

For individuals allocated to the blue-depleted light conditions, adherence with the intervention is assessed using an item checklist to record any exposure to normal lighting (duration and reasons), whether blue-blocking glasses were worn as appropriate (e.g., when exiting the unit) and whether blue-blocking filters were employed on media devices.

3.2.2 Withdrawn from study

Randomisation occurs at the point of admission which means that all withdrawals are post-randomisation. Participants withdrawn from the study for the following reasons will be removed from further analyses:

Immediately post randomisation:

- Lack of availability of rooms for the allocated light-condition
- Clinical imperative: A senior clinician decides that admission to the allocated room is inappropriate, e.g. due to case mix within the ward, staff-to-patient ratios

Any time during admission:

- Unwilling to give written informed consent at any time during admission
- Unable to give informed consent for the duration of the stay
- Consent procedure was incomplete
- Declines participation at any stage during the study

3.2.3 Protocol deviations

During the admission withdrawal may occur because:

- The participant is absent for >24 hours from the ward to which they were randomised, for example due to transfer to another hospital for medical/somatic reasons. Any participant who is absent from the ward voluntarily is considered to have been discharged and if they were to return they would be re-randomised and recorded as another admission.
- Clinical concerns regarding an individuals' participation

These scenarios will be considered protocol deviations, and the participants will be removed from any per-protocol analyses (see also §3.3.2).

3.3 Analysis populations

3.3.1 Intention-to-treat population

The intention-to-treat (ITT) population will include all participants who were randomised and provided informed written consent and excluding those withdrawn for reasons outlined in §3.2.2.

STATISTICAL ANALYSIS PLAN for BAB-study

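### The primary analysis set labelled intention-to-treat is a modified set: it drops randomised patients, even consented ones, for reasons concerning the allocated room

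*SAP*

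**What the plan says.** SAP 5.1 analyses the primary outcome, length of stay, in the ITT population. SAP 3.3.1 defines that population as "all participants who were randomised and provided informed written consent and excluding those withdrawn for reasons outlined in §3.2.2".

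SAP 3.2.2 states the consequence of such a withdrawal: "Participants withdrawn from the study for the following reasons will be removed from further analyses". It lists six reasons in two groups.

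- Directly after randomisation: "Lack of availability of rooms for the allocated light-condition", and a clinical imperative, in which "A senior clinician decides that admission to the allocated room is inappropriate". Case mix and staffing are the only examples given.
- At any point in the stay: unwillingness to consent, "Unable to give informed consent for the duration of the stay", an incomplete consent procedure, and "Declines participation at any stage during the study".

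SAP 3.2.3 treats absence of more than 24 hours and clinical concerns arising during the stay as protocol deviations. Those patients leave only the per-protocol set. SAP 3.2 explains that the published protocol did not separate the two kinds of withdrawal, so this sorting was done in the SAP.

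On timing and masking, SAP 2.2 says "patients will be randomised prior to arrival at the unit" and SAP 2.1 says "This is a single-centre, unblinded, two-arm, parallel-group".

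**The concern.** An intention-to-treat set keeps every randomised patient in the arm drawn, whatever happens next. This set does not.

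A failed placement is the kind of event that intention-to-treat analysis is meant to absorb, yet both room-related reasons take the patient out. Written consent is already a separate condition in 3.3.1, so the further exclusion clause removes such patients even when they consented. The SAP is also uneven: a clinician's decision at the door removes a patient from the primary analysis, while a clinician's concern later in the stay does not.

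The consent and participation reasons can arise after the patient has lived in a known lighting condition. One of them, incapacity lasting the whole stay, ties inclusion to the stay whose length is the outcome.

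A superiority result labelled ITT would be read as fully protected by randomisation. The comparison carries that protection only if the exclusions are alike in both arms or unrelated to prognosis.

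**Working it through.** **The definitions side by side**

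| Event after randomisation | SAP section | In primary set? | In per-protocol set? |
|---|---|---|---|
| No room in allocated condition | 3.2.2 | No, even if consented | No |
| Clinician rejects allocated room on entry | 3.2.2 | No, even if consented | No |
| Consent refused, not possible or incomplete; participation declined | 3.2.2 | No | No |
| Clinical concern later in stay; absence over 24 hours | 3.2.3 | Yes | No |

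The per-protocol set (3.3.2) is a subset of the primary set, so repeating the analysis there (5.1.3) restores nobody. The CONSORT diagram and the reasons by arm (4.1) count exclusions. The comparison in 5.3 concerns the proportion transferred. None of these analyses length of stay in the excluded patients.

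**Possible bias.** The SAP gives no exclusion rates and no figure for length of stay, so there is nothing to reproduce and every input below is assumed. Let q be the fraction of an arm excluded, μ the arm's full mean, and d the excess stay in days of the excluded over μ. From μ = (1 − q) × retained mean + q × (μ + d),

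retained mean = μ − q·d/(1 − q).

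With no true effect, bias (A − B) = −qA·dA/(1 − qA) + qB·dB/(1 − qB).

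| Excluded, A vs B | Excess d, A vs B | Arithmetic | Bias (days) |
|---|---|---|---|
| 10% vs 10% | 4 vs 4 | −0.444 + 0.444 | 0 |
| 15% vs 5% | 0 vs 0 | 0 + 0 | 0 |
| 10% vs 5% | 4 vs 4 | −0.444 + 0.211 | −0.23 |
| 10% vs 5% | −4 vs −4 | +0.444 − 0.211 | +0.23 |
| 15% vs 5% | 4 vs 4 | −0.706 + 0.211 | −0.50 |
| 15% vs 5% | −4 vs −4 | +0.706 − 0.211 | +0.50 |
| 10% vs 10% | 4 vs 0 | −0.444 + 0 | −0.44 |

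The last row shows that equal rates do not protect if the type of patient excluded differs. If the covariates in 5.1 explained half the excess (d = 2), the 10% versus 5% and 15% versus 5% figures would fall to 0.12 and 0.25 in absolute value. A simulation with exponential stays (assumed mean 8 days, 4 million draws per arm) gave −0.232 and −0.498 for the two d = +4 cases with unequal rates.

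**What keeping consented patients would recover.** If a share f of the excluded is recovered, q becomes q(1 − f). For 15% versus 5% and d = 4:

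- f = 0: bias −0.50
- f = 0.25 (11.25% vs 3.75%): −0.507 + 0.156 = −0.35
- f = 0.5 (7.5% vs 2.5%): −0.324 + 0.103 = −0.22
- f = 1: 0

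This treats recovered patients as typical of the excluded. If those who consented are a selected few, the gain need not follow.

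**What it would cost.** If fractions rA and rB of the arms received the other condition, 1 − rA − rB of a true difference remains. With 5% in each arm, 1 − 0.05 − 0.05 = 90%. With 15% and 5%, 1 − 0.15 − 0.05 = 80%. The second figure belongs beside the full-recovery case above, if all recovered patients crossed over.

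**The case against.** The definition is open. The SAP states the restriction in one sentence, lists every reason, and commits to a CONSORT diagram and reasons by arm, so a reader of the report would see any imbalance. That stands: the fault lies in the label and the set definition, and nothing is concealed.

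Much of the exclusion follows from the design. With randomisation before arrival, consent can only come afterwards, and patients who never consent may have to be left out. The reasons themselves come from the published protocol. This also stands, but it covers neither the two room-related reasons in a consented patient nor the ITT label.

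A reader might infer that the exclusions differ between arms because they depend on the room drawn. The SAP does not support this. Both reasons are worded alike for either arm and act before exposure. The wards share layout and facilities (1.3.1), and the override examples are ward-level. Room shortage may well be unrelated to prognosis.

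A reader might also infer that keeping consented patients would restore a true ITT analysis. It would not. The immediate withdrawals may mostly precede consent and data collection is over (2.6), so few or none may be recoverable.

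**Conclusion.** The set in 3.3.1 is not intention-to-treat. It is randomised, consented and not withdrawn under 3.2.2, and it removes consented patients for two non-consent reasons that arise after randomisation. That much is certain from the text, as is the absence of any planned analysis of length of stay that includes the excluded patients.

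Bias in the result is a risk and has not been shown. It needs exclusions that differ between arms in rate or in type of patient, and the SAP gives no information on either. The range of 0 to about 0.5 days in either direction rests wholly on assumed rates and an assumed 4-day excess. It illustrates the mechanism and does not estimate this trial's bias. The point should be fixed as a matter of labelling, set definition and reporting; it does not show that the comparison is invalid.

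**What to change.** Amend the SAP, before unblinding if that is still possible. The amendment route in 3.4.2 covers model checks and the choice of final model, so a change of population needs its own stated reason.

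1. Rename the primary set 'modified ITT (consented)' and limit the conclusion to it. This is a change of wording.
2. Report exclusions by arm and reason, and give consent status for the room and clinician withdrawals. This adds one row to a table already planned, and shows whether item 3 has any content.
3. Move the two immediate reasons from 3.2.2 to 3.2.3. Any patient who gave and did not withdraw written consent is then analysed in the allocated arm and removed only from per-protocol. This needs only admission and discharge dates, which 5.1.1 says come from hospital records. The amendment should state that it may recover few or no patients, and that it dilutes the effect where they received the other condition (90% of the difference left with 5% crossing in each arm, 80% with 15% and 5%). Patients who later decline participation stay excluded.
4. Only where existing approvals allow, add a sensitivity comparison of length of stay by allocated arm in all randomised admissions. The SAP does not show whether they do.
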